## 15.2. FDG-PET CT

A pre-chemo-radiotherapy whole body FDG-PET-CT will be taken before enrolment to assess background FDG avidity in the tumour, the hilar and mediastinal lymph nodes (if involved at staging), and the lungs. If FDG-PET CT is not available, contrast enhanced CT of the thorax and upper abdomen (incl. liver, kidney, adrenals) and bone scan is required for tumour assessment at baseline.

FDG-PET CT images must be stored locally in electronic format for later central review, please consult the *STIMULI procedures manual* for detail.

## 15.3. Optional evaluations

A biobank will be created with centralised samples for translational research. Tumour blocks, PBMCs (selected centres only), whole blood and mandatory serum sample will be centrally collected and biobanked at the Ludwig Institute for Cancer Research at University of Lausanne, Switzerland.

### 15.3.1. Blood sample

Whole blood samples will be taken at baseline, at randomisation and 9 and 18 weeks (+/- 3 days) after randomisation, as follows:

- 2.5 mL in PAXgene tubes for RNA profiling;
- At selected sites: 50 mL in lithium heparin tubes for immunomonitoring with blood cell subtyping and quantification, including FACS analysis.

For details on blood collection and processing of samples, please consult the *STIMULI procedures manual*.

### 15.3.2. FFPE material

A diagnostic tumour FFPE block, or a cell block if the diagnosis is done by cytology, will be collected from all consenting patients. If requested, these blocks can be returned to the submitting site after the slides for the analyses have been cut. If no blocks can be submitted, 5-10 sections with a minimum thickness of 15-20µm from the tumour block or cell block can be submitted instead. If further slides can be provided, 5 sections at 4-5 µm thickness should also be submitted for immunohistochemistry characterization. All slides should be freshly cut.

Progressing patients will be asked for a voluntary re-biopsy, if possible not in an irradiated area to avoid fibrotic tissue.

### 15.3.3. Translational research

The following projects will be considered, at least, and subsequently adapted according to the growing knowledge about immunological modification observed and potential biomarkers of nivolumab plus ipilimumab immunotherapy:

- Presence of infiltrating lymphocytes in tumour (TILs) will be evaluated. Study and characterisation of TILs in detail will be performed using flow cytometry and functional in vitro assays.
- Tregs and T effectors quantitative analyses by FACS
- Immune modulation on respective lymphocyte subtypes by FACS
- Measurement and characterisation of T-cell infiltration, T-cell subsets and activation, and immune activation using multispectral immunohistochemistry (IHC) to quantify immune cell subsets. Immunohistochemistry on tumour micro-environment for immune cell infiltration description.
- Gene expression profile (targeting selected panel of immune-related genes) will be analysed by deep sequencing, using Next Generation Sequencing technology including TCR sequencing to capture clonal expansion of TILs.
- Multiple tumour, inflammatory- and immune-related genes will be analysed by multiplex Nanostring technology.
- PD-L1 expression

#### **15.4. Submission of material**

The tissue and blood samples collected during the conduct of the trial must be marked with the patient identifier issued by the RDE system and shipped to the central reference laboratory (Ludwig Institute for Cancer Research, University of Lausanne, Switzerland) and will be stored there for an unlimited time. This precious material will be used for central quality assurance and made available for translational research projects.

##### 15.4.1. Submission of FFPE material

The following items should be submitted for all patients:

1. Pathology Report from diagnostic biopsy (all information allowing identification of the patient, e.g. patient name, day and month of birth, must be removed)
2. Tumour block or cell block from diagnostic biopsy, or alternatively 5-10 sections of at least 15-20  $\mu\text{m}$  from the tumour block or cell block, and, when feasible, also 5 freshly cut sections at 4-5  $\mu\text{m}$  thickness.

Recommended, but not required:

3. Pathology report from re-biopsy at progression (all information allowing identification of the patient, e.g. patient name, day and month of birth, must be removed)
4. Tumour or cell block from re-biopsy at progression, or alternatively 5-10 sections of at least 15-20  $\mu\text{m}$  from the tumour block or cell block, and, when feasible, also 5 freshly cut sections at 4-5  $\mu\text{m}$  thickness.

Paraffin-embedded cell blocks are a valuable alternative to tumour blocks. Cytology smears alone are not accepted in this trial. Tumour material should be submitted as soon as obtained, and documented in the Biological Material Tracking eCRF in the database. If requested, these blocks can be returned to the submitting site after the slides for the analyses have been cut.

Alternatively, 5-10 sections of at least 15-20µm will be acceptable if the tumour block is not available for banking. If further slides can be provided, 5 freshly cut sections at 4-5 µm thickness should also be submitted.

All reports, slides, and blocks must be marked with the patient identification number issued by the RDE system. The pathology number, and any other identification should be removed or blackened.

Please ensure that the blocks and/or slides are carefully packaged as otherwise they could easily get damaged during transport.

Samples have to be sent to:

Ludwig Center for Cancer Research  
Hôpital Orthopédique HO 05/1552  
[name]  
[name], Switzerland

Anonymised pathology reports should be uploaded via the RDE system. Please consult the *STIMULI procedures manual* for specific instructions.

#### 15.4.2. Submission of blood and serum samples

Blood collection and serum preparation (see *STIMULI procedures manual*):

- 2.5 mL whole blood will be put into PAXgene tubes (Qiagen; for gene profiling) and stored locally at -80°C.
- Serum samples taken from 5mL blood should be immediately frozen at -80°C
- 50 mL blood will be collected to isolate PBMCs (in selected centers only)

Samples will be kept at the participating site until shipment. Shipments will be arranged centrally. Samples have to be sent to the same address as indicated above (section 15.4.1).

### 15.5. Banking of biological material

ETOP has established a central repository for tissue blocks/slides, PBMCs, whole blood and serum samples from every patient enrolled in this trial. The required pathological material (described in the previous section) is submitted to, catalogued, and maintained at the Ludwig Institute for Cancer Research, University of Lausanne, Switzerland, and will be made available for translational research, following completion of the primary trial translational research objectives.

## 16. Trial procedures

This section gives an overview of procedures, clinical and laboratory evaluations and follow-up investigations.

## 16.1. Trial phases

The trial consists of the following phases:

16.1.1. **Screening:** Baseline evaluations must be done within 28 days prior to enrolment (if the first chemotherapy cycle has been administered before enrolment, baseline evaluations must have been done within 35 days before start of first chemotherapy cycle). Please consult the *STIMULI procedures manual* for details.

### 16.1.2. Chemotherapy-radiotherapy:

**Chemotherapy:** will be started in the week following enrolment (alternatively, maximum 1 cycle of chemotherapy may be administered before enrolment) and consists of 4 cycles of cisplatin (25 mg/m^2 i.v. on days 1 - 3 or 75 mg/ m^2 on day 1) or carboplatin (AUC 5-6, calculated according Calvert formula, i.v. on day 1), plus etoposide (100 mg/ m^2 i.v. on days 1 – 3), repeated every 3 weeks (+/- 3 days without cycle delay).

**Thoracic radiotherapy:** Two different radiation doses are allowed: the recommended schedule is 45 Gy in 30 twice-daily fractions of 1.5 Gy (6-8 hours apart), in 30 treatments on 5 days per week over 3 weeks (preferred). The alternative, but not-recommended schedule is 56 Gy, given in 28 once-daily fractions of 2 Gy, 5 days per week over 6 weeks. Radiotherapy should start on day 1 of chemotherapy cycle 1 or on day 1 of chemotherapy cycle 2. Radiotherapy start on day 1 of cycle 3 is allowed as an exception if patient is enrolled after the first cycle only.

**Prophylactic cranial irradiation (PCI):** 25 Gy in 10 fractions starting between day 8 and day 15 of first day of chemotherapy cycle 4 and finished not later than day 29 from start of cycle 4.

16.1.3. **Consolidation phase:** Nivolumab plus ipilimumab combination therapy (induction) is to start within 6-8 weeks (42-56 days) from start of chemotherapy cycle 4, and not more than 2 weeks (14 days) after the date of randomisation.

#### a) Induction:

- Nivolumab at a dose of 1 mg/kg i.v. over a period of 30 minutes followed (on the same day) by
- Ipilimumab at a dose of 3 mg/kg i.v. over a period of 90 minutes once every 3 weeks (+/- 3 days, without dosing delay), for 4 cycles

#### b) Maintenance:

Nivolumab at a dose of 240 mg i.v. over a period of 30 minutes, once every 2 weeks (+/- 2 days, without dosing delay) for maximum 12 months from start of maintenance phase. The first dose of maintenance nivolumab will be administered 3 weeks after the last IMP doses of induction phase

Upon disease progression or completion of trial treatment, further therapy will be at the discretion of the treating physician.

16.1.4. **End of treatment:** an end of treatment visit will occur within 30 days following the last administered dose of trial treatment. For patients in the observation arm the end of treatment visit is to be scheduled within 30 days following PD or 15 months after randomisation. For patients who have not been randomised the end of treatment visit is to be scheduled within 30 days following PD or within 30 days following the last chemotherapy cycle.

16.1.5. **Follow-up period**

16.1.5.1. Before tumour progression: In the first 18 months after randomisation follow-up visits will occur together with the CT scans according to the schedule indicated in section 13.2, then every 12 (+/- 1) weeks until PD for a maximum of 4.5 years after the enrolment of the last patient.

16.1.5.2. After tumour progression: follow-up visits will occur every 12 weeks in the first year after randomisation starting from date of progression, then every 6 months up to 4.5 years after the enrolment of the last patient. This applies also to patients who have been enrolled but not randomised (see section 18.4).

**16.2. Baseline evaluations**

To be done within 28 days prior to enrolment. If the first chemotherapy cycle has been administered before enrolment, baseline evaluations must have been done within 35 days before start of first chemotherapy cycle.

16.2.1. Obtain written informed consent prior to any trial-specific evaluations or interventions

16.2.2. Medical history including symptoms, smoking history, medications, comorbidities and allergies

16.2.3. Physical examination including blood pressure [mmHg], ECOG performance status (see definition in *STIMULI procedures manual*), and body weight [kg], height [cm]

16.2.4. Haematology: haemoglobin, platelets, complete white blood cell count (leukocytes, neutrophils, eosinophils, basophils (or total granulocytes), lymphocytes and monocytes)

16.2.5. HIV, hepatitis B and C status

16.2.6. Renal function: serum creatinine and creatinine clearance calculated according to Cockcroft-Gault

16.2.7. Hepatic function: ALT, AST, AP, bilirubin

16.2.8. Pulmonary function: relative FEV1 and DLCO (%)

16.2.9. Pregnancy test for women with childbearing potential within 7 days before chemotherapy start.

16.2.10. Whole body FDG-PET-CT (with max SUV measurements) including a contrast-enhanced CT of thorax and upper abdomen (incl. liver, kidney, adrenals), see procedure manual and *STIMULI CRF completion guidelines* for details;

*OR*

contrast-enhanced CT of thorax and upper abdomen (incl. liver, kidney, adrenals) and bone scan;

16.2.11. TNM categories

16.2.12. Brain MRI (or contrast enhanced CT of the brain)

16.2.13. FFPE block from diagnosis available for biobanking (subject to additional consent). If no blocks can be submitted, 5-10 sections with a minimum thickness of 15-20µm from the tumour block or cell block can be submitted instead. Submission of additional 5 freshly cut sections at 4-5 µm thickness is desired.

16.2.14. Mandatory serum sample, whole blood sample (subject to additional consent).

### **16.3. During chemo-radiotherapy**

To be done within 24 hours of each chemotherapy administration

16.3.1. Physical exam: blood pressure, performance status and body weight

16.3.2. Haematology: haemoglobin, platelets neutrophils

16.3.3. Hepatic function: AST, bilirubin

16.3.4. Renal function: serum creatinine and creatinine clearance (calculated according to Cockcroft-Gault)

Recording symptoms, adverse events, concomitant medications.

### **16.4. Before randomisation**

Contrast-enhanced CT of thorax and upper abdomen (incl. liver, kidney, adrenals) should take place within 14 days before randomisation.

All other examinations, listed below, should take place within 7 days before randomisation:

16.4.1. Physical examination including blood pressure, performance status, and body weight

16.4.2. Haematology: haemoglobin, platelets, complete white blood cell count (leukocytes, neutrophils, eosinophils, basophils (or total granulocytes), lymphocytes and monocytes)

16.4.3. Hepatic function: AST, ALT, AP, bilirubin

16.4.4. Renal function: serum creatinine plus creatinine clearance (calculated according to

Cockcroft-Gault)

16.4.5. Recording of symptoms, adverse events and concomitant medications

16.4.6. Pregnancy test

### **16.5. Before start of consolidation phase**

16.5.1. Serum sample; whole blood sample (subject to additional consent);

### **16.6. During consolidation phase (induction and maintenance)**

Within 3 days before the administration of the next dose, the following evaluations will be done.

In the observation arm, these evaluations should be done 9 and 18 weeks (+/- 3 days) after randomisation and thereafter every 18 weeks (+/- 1 week), according to local standard of follow-up, until PD or for maximum 15 months after randomisation. Beyond these 15 months or upon PD patients will enter the follow-up phase..

16.6.1. Recording of symptoms, adverse events and concomitant medications.

16.6.2. Physical examination including blood pressure, performance status, and body weight

16.6.3. Haematology: haemoglobin, platelets, complete white blood cell count (leukocytes, neutrophils, eosinophils, basophils (or total granulocytes), lymphocytes and monocytes)

16.6.4. Renal function: serum creatinine and creatinine clearance (calculated according to Cockcroft-Gault)

16.6.5. Hepatic function: ALT, AST, AP, Bilirubin

16.6.6. Na, K

16.6.7. Serum sample; whole blood (subject to additional consent) at 9 and 18 weeks (+/- 3 days) after randomisation.

16.6.8. A serum or urine pregnancy testing is required every 6 weeks during consolidation treatment (only in experimental arm).

16.6.9. Ca, LDH, Glucose, amylase, lipase (only in experimental arm). To be done before each administration of nivolumab and ipilimumab during induction phase and then before every 3rd administration of nivolumab during maintenance phase.

16.6.10. TSH (only in the experimental arm). To be done before the 1st and the 3rd administration of nivolumab and ipilimumab during induction phase and before the 1st and then every 3rd administration of nivolumab in the maintenance phase (always within 3 days prior to next IMP dose). In case of abnormal TSH, also free T3 / T4 have to be measured. In case a value is abnormal then free T3/T4 needs to be repeated before the next administration.

**Note:** For both treatment arms, post randomisation CT scans of thorax and upper abdomen

(incl. liver, kidney, adrenals) have to be repeated as indicated below, until tumour progression:

- up to 18 months: every 9 weeks 9, 18, 27, 36, 45, 54, 63, 72, 81 (+/- 1 week)
- up to 2 years: every 12 weeks 93, 105 (+/- 1 week)
- years 3 and 4: every 6 months (26 weeks) 131, 157, 183, 209 (+/- 1 week)
- at 5 years: 260 (+/- 1 week)

In case of early local tumour progression documented by CT scan 9 weeks after randomisation, a radiographic assessment / scan should be performed at least 4 weeks after the original PD scan to determine whether there has been a decrease in the tumour size or disease stabilisation, or alternatively continued PD which would terminate the trial treatment. Please consult the *STIMULI procedures manual* for a detailed schedule.

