- 1 ≤ 28 days prior enrolment; if the first chemotherapy cycle has been administered before enrolment, baseline evaluations must have been done within 35 days before start of first chemotherapy cycle.
- 2 **Chemotherapy** consists of platinum compound (cis- or carboplatin) and etoposide combination and is given for 4 cycles (1 cycle = 21 days). Chemotherapy should start within 7 days after enrolment. If the start of chemotherapy cannot be delayed, a maximum of 1 chemotherapy cycle can be administered before enrolment.
- 3 **Randomisation** should take place 5 - 6 weeks from day 1 of chemotherapy cycle 4 (between days 35 and 42 of cycle 4). All examinations have to be done within 7 days prior randomisation (except for tumour assessment, which has to be done within 14 days before randomisation).
- 4 **Consolidation treatment** should start 6-8 weeks (42-56 day) from start of chemotherapy cycle 4, and not more than 2 weeks (14 days) after the date of randomisation.
- 5 **Induction phase:** nivolumab (1 mg/kg i.v. over a period of 30 minutes) followed (on the same day) by ipilimumab (3 mg/kg i.v. over a period of 90 minutes), once every 3 weeks (+/- 3 days, without dosing delay), for 4 cycles.
- 6 **Maintenance phase:** nivolumab (240 mg i.v. over a period of 30 minutes), once every 2 weeks (+/- 2 days, without dosing delay) until PD, for a maximum of 1 year from start of maintenance phase. The first dose of maintenance nivolumab will be administered 3 weeks after the last IMP doses of induction phase.

- 7 **Observation arm:** patients should be documented 9 and 18 weeks (+/- 3 days) after randomisation and thereafter every 18 weeks (+/- 1 week), according to local standard of follow-up, until PD or for maximum 15 months after randomisation. The following laboratory values are to be measured: haematology, renal function, hepatic function, Na and K. Beyond 15 months after randomisation or upon PD patients will enter the follow-up phase.  
CT scans for tumour assessment are done at the same schedule as for patient in the experimental arm (see footnote 13).
- 8 **Follow-up:**  

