Before PD: Patients who completed consolidation treatment (in the observation arm this corresponds to 15 months after randomisation) or discontinued IMP treatment before tumour progression should have physical examination at regular intervals (blood pressure, performance status and weight). In the first 18 months after randomisation this has to be done together with the CT scans according to the schedule indicated in footnote 13, then every 12 (+/- 1) weeks until PD for a maximum of 4.5 years after the enrolment of the last patient.  
After PD: Patients with tumour progression will end trial treatment and should have documented survival, and further lines of treatment every 12 weeks (+/-1 week) starting from date of progression during the first year after randomisation, then every 6 months (+/- 4 weeks) up to 4.5 years after the enrolment of the last patient.
- 9 **Haematology:** haemoglobin, platelets, complete white blood cell count [leucocytes, neutrophils, eosinophils, basophils (or total granulocytes), lymphocytes, monocytes]
- 10 **Only patients in experimental arm.** In case of abnormal TSH value, also free T3 and T4 has to be measured.
- 11 **Pregnancy test:** Women of childbearing potential, including women who had their last menstrual period in the last 2 years, must have a negative serum or urine pregnancy test within 7 days before beginning of chemotherapy. The test has to be repeated within 7 days before randomization and then every 6 weeks during consolidation treatment. Pregnancy tests should be repeated at approximately 30 days and approximately 70 days after consolidation treatment stop.
- 12 **Tumour assessments before randomisation**  
At baseline: brain MRI (or contrast enhanced CT of the brain), *AND* whole body FDG-PET CT including a contrast-enhanced CT of thorax and upper abdomen (incl. liver, kidney, adrenals). If FDG-PET CT is not available, contrast enhanced CT of the thorax and upper abdomen (incl. liver, kidney, adrenals) and bone scan is required for tumour assessment at baseline.  
Within 14 days prior to randomisation: contrast-enhanced CT of thorax and upper abdomen (incl. liver, kidney, adrenals)
- 13 **Tumour assessments after randomisation**  
 For both treatment arms, CT of thorax and upper abdomen (incl. liver, kidney, adrenals) have to be done as indicated below:
- |                           |                           |                            |  |

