#### 11.2.3. Safety

Nivolumab monotherapy in patients with SCLC was well tolerated. 52.5% of the patients had drug-related AEs of any grade, 15.0% with Grade 3-4 events (Table 12). There were no drug related adverse AEs leading to death. The most frequent ( $\geq 10\%$ , any grade) drug-related AEs were fatigue, diarrhoea, nausea, and decreased appetite (Table 12). A total of 7.5% of patients permanently discontinued treatment because of treatment related AEs (N = 3, limbic encephalitis, hyperglycemia, and stomatitis).

Nivolumab plus ipilimumab combination therapy showed a manageable safety profile. While the incidence of drug-related AEs (nivolumab 1 mg/kg plus ipilimumab 3 mg/kg: 76.6% any grade, 34% Grade 3-4) was higher than in the nivolumab monotherapy group (Table 12), the treatment discontinuation rate for treatment related AEs was 11% (nivolumab 1 mg/kg plus ipilimumab 3 mg/kg): N = 5, diarrhoea, myasthenia gravis [subsequently developing complications with fatal outcome], pneumonitis, cardiomyopathy, one patient with hypothyroidism, hyperglycemia and increased ALT). The most frequent ( $\geq 10\%$ , any grade) drug-related AEs

were diarrhoea, fatigue, rash, pruritus, hypothyroidism, rash maculo-papular, nausea, hyperthyroidism, and lipase increased (Table 12).

One treatment-related death in the nivolumab 1 mg/kg plus ipilimumab 3 mg/kg cohort occurred. This patient developed myasthenia gravis (reported as Grade 4) after treatment start and suffered from complications causing the patient's death.

Limbic encephalitis was reported in 3 patients and resolved with immunosuppressive treatment in 2 cases. Another patient had a minor response to immunosuppressive treatment and eventually died due to the underlying tumour disease.

**Table 12: Drug-related AEs  $\geq$ 5% (any grade) and all Grade 3-5 AEs – SCLC patients treated with nivolumab monotherapy or nivolumab 1 mg/kg plus ipilimumab 3 mg/kg combination therapy**

System organ class (%)	Nivolumab (N = 40)			Nivolumab 1 mg/kg + ipilimumab 3 mg/kg (N = 47)		
	Any grade	Grade 3-4	Grade 5	Any grade	Grade 3-4	Grade 5
Total patients with an event	21 (52.5)	6 (15.0)	0	36 (76.6)	16 (34.0)	0
Gastrointestinal disorder	10 (25.0)	1 (2.5)	0	19 (40.4)	6 (12.8)	0
Skin and subcutaneous tissue disorder	6 (15.0)	0	0	21 (44.7)	4 (8.5)	0
General disorders and administration site conditions	7 (17.5)	1 (2.5)	0	11 (23.4)	0	0
Endocrine disorders	2 (5.0)	0	0	10 (21.3)	0	0

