### **12.3. Definition of immune-related Adverse Events (irAE)**

The following adverse events are of special interest and must be documented after randomisation in both treatment arms:

CTCAE Version 4.0 system organ class / preferred terms:

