4.7 Safety analysis

The safety analysis will be based on the safety cohort, i.e., all patients who have received at least 1 dose of IMP treatment (experimental arm) plus all patients randomized to observation arm, and will include the following:

- Overview of the number of patients who experienced an AE and/or a SAE, as well as
 the number of patients in the safety cohort who did not experience an event, along with
 respective percentages will be shown. This information will be presented overall and by
 treatment arm. Also, number of patients that entered the study with baseline symptoms
 will be reported.
- Number of AEs/SAEs will be presented overall and by treatment arm.
- Number of patients experiencing a specific number of AEs/SAEs, overall and by treatment arm.
- Distribution of (S)AEs by grade and CTCAE category, separately for the two treatment arms. Six columns, one for each grade and one for all (any) grades, will be shown (for each arm). An additional column (by arm) indicating which events were also SAEs will be also available. In this column, the frequency of the SAEs and the severity grade will be given. The percentages that will accompany the frequencies will be based on the respective frequency of an event over the total number of patients in the safety cohort and specific treatment arm. This table will include all (S)AEs irrespective of their relation to the trial treatment.
- Analogous table focusing only on the treatment related (S)AEs.
- Number and corresponding percentages of treatment related (S)AEs by grade, leading either to treatment discontinuation or death will be summarized for the two treatment arms.

- Maximum severity of adverse events (AE/SAE) for patients, overall and by treatment arm.

- Number of SAEs by center
- Detailed information of pulmonary AEs/SAEs of grade ≥3 will be summarized for the two treatment arms.
- The risk difference between the two treatment arms, along with corresponding 95%
 CIs for specific adverse evets (most frequent i.e. ≥15%, of any grade, or perhaps focus on grade ≥3, irrespective of relation to treatment or treatment-related).

Analogous (more concise) information will be reported for the adverse events during the chemo-radiotherapy phase of all enrolled patients who received at least one dose of chemo-radiotherapy (per-protocol safety cohort).

5 Technical details

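### TSH and the calcium, LDH, glucose, amylase and lipase panel are scheduled in the experimental arm only, so any-grade between-arm risk differences for events they detect would partly reflect who was tested

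*Protocol*

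**What the plan says.** **Testing.** Protocol 16.6.10 has "TSH (only in the experimental arm"), at the first and third induction doses, at the first maintenance dose and at every third one thereafter. Section 16.6.9 has "Ca, LDH, Glucose, amylase, lipase (only in experimental arm"), at every induction dose and every third maintenance dose. Footnote 10 of the trial schedule (section 2) repeats the restriction for both rows: "Only patients in experimental arm". Footnote 7 gives the observation-arm bloods: "The following laboratory values are to be measured: haematology, renal function, hepatic function, Na and K". The text of 16.2 (baseline), 16.4 (before randomisation) and 16.8 (end of treatment) lists none of the six analytes.

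**Visits.** Section 16.6 ties experimental-arm evaluations to each dose. For the other arm it says: "In the observation arm, these evaluations should be done 9 and 18 weeks (+/- 3 days) after randomisation and thereafter every 18 weeks", up to 15 months.

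**Comparison.** Protocol 12.3 introduces its list, which includes hypothyroidism, with: "The following adverse events are of special interest and must be documented after randomisation in both treatment arms". Protocol 18.4 compares the arms on tolerability. SAP 4.7 tabulates events by arm, grade and CTCAE category, with all patients of the arm in the safety cohort as denominator. It then plans: "The risk difference between the two treatment arms, along with corresponding 95"% intervals, for the most frequent events (at least 15%, any grade, with a possible focus on grade 3 or higher), whether or not they are considered related to treatment.

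**The concern.** A low-grade thyroid, pancreatic-enzyme or glucose abnormality is often found only because someone ran the test. If the test is scheduled about a dozen times in one arm and never in the other, background cases are counted more completely in the experimental arm. The SAP's denominators are all patients in the arm, not patients tested, so nothing in the calculation corrects for this. Equal follow-up or equal visit counts would not cure it either.

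At stake is the reading of a secondary safety result. A risk difference with a confidence interval looks like a treatment effect, and for these terms it would be a treatment effect plus a detection effect, in the direction of excess toxicity with nivolumab plus ipilimumab.

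**Working it through.** The plan states no figure for this point, so there is none to reproduce. The check has three steps.

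**1. Scheduled tests for a patient completing treatment.** Maintenance doses: 52 weeks / 2 = 26, after 4 induction doses.

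- TSH: 2 in induction, plus maintenance doses 1, 4, ..., 25 = 9. Total 11, against 0.
- Panel: 4 in induction, plus maintenance doses 3, 6, ..., 24 = 8. Total 12 (13 if counted from dose 1), against 0.

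**2. Which terms could reach the SAP's cut.** Protocol 11.2.3 says that the drug-related events seen in at least 10% of SCLC patients on this combination "were diarrhoea, fatigue, rash, pruritus, hypothyroidism, rash maculo-papular, nausea, hyperthyroidism, and lipase increased (Table 12"). Table 12 gives endocrine disorders in 10/47 = 21.3%, none of grade 3-4.

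- The list uses 10%; the SAP uses 15%. To be listed, hypothyroidism and hyperthyroidism each need at least 5/47 = 10.6%. If no patient had both, 10 endocrine patients in all means exactly 5 each, below 15%. With overlap, either could be higher. The documents do not say.
- No separate rate is given for raised lipase. The metabolism class as a whole was 7/47 = 14.9%.
- The SAP does not say whether 15% applies within an arm or to both arms pooled. If pooled at 1:1 with almost no observation-arm cases, about 30% would be needed in the experimental arm.

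**3. Size of the detection effect.** Let the true incidences be p1 (experimental) and p0 (observation), with every case found in the experimental arm and a fraction s found in the observation arm. The apparent difference is p1 - s·p0, the true one is p1 - p0, and the excess is p0(1 - s). The values of p0 and s are assumptions.

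| p0 | s = 0.75 | s = 0.50 | s = 0.25 |
|---|---|---|---|
| 5% | 1.25 points | 2.5 | 3.75 |
| 10% | 2.5 | 5.0 | 7.5 |
| 20% | 5.0 | 10.0 | 15.0 |

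*No true difference.* Take p1 = p0 = 20% and the planned 130 per arm (260 / 2). The Wald standard error is the square root of [0.20 × 0.80 + 0.20s(1 - 0.20s)] / 130.

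- s = 0.50: +10 points (95% CI 1.4 to 18.6).
- s = 0.25: +15 points (7.2 to 22.8).
- s = 0.75: +5 points (-4.2 to 14.2).

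Accrual closed early and the documents do not give the final number. At an assumed 75 per arm, s = 0.25 gives +15 points (4.7 to 25.3) and s = 0.50 gives +10 points (-1.3 to 21.3). The interval can therefore exclude zero with no true difference, but only under the less favourable assumptions.

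*A real drug effect.* Take p1 = 21.3% (the endocrine rate in Table 12) and an assumed p0 of 5%. The true difference is 21.3 - 5.0 = 16.3 points. The apparent difference is 21.3 - 5s: 17.55 points at s = 0.75, 18.8 at s = 0.50 and 20.05 at s = 0.25. Detection then adds 1.25 to 3.75 points. This term would meet a 15% cut applied within an arm, but not a pooled one: at s = 0.75 the pooled rate is (21.3 + 3.75) / 2 = 12.5%.

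**The case against.** Testing before each dose is drug-specific safety monitoring, and having no counterpart in an untreated open-label control arm is a defensible choice. That stands: the schedule is not the fault, only the unqualified contrast.

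The reach is limited, and this too stands. The risk difference covers only frequent events, and the 10% list does not show that any of these terms reaches 15%. The SAP's own option of focusing on grade 3 or higher would largely remove thyroid events, since Table 12 has no grade 3-4 endocrine event. Protocol 12.1 records laboratory abnormalities of non-safety parameters as adverse events only from grade 3. It does not define such parameters, but the rule may keep low-grade lipase, amylase, glucose, calcium and LDH findings out of the data. It would not remove a diagnosis of hypothyroidism, which 12.3 names.

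A reader might infer that the observation arm cannot yield these events at all. The documents do not support that: its visits record symptoms and adverse events and follow local practice, and local testing is not forbidden. So s is unknown, not zero.

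A reader might also infer that 12.3 conflicts with 16.6 for all six analytes. It does not: its list names endocrine terms, but no amylase, lipase, glucose, calcium or LDH term.

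Finally, the bias overstates toxicity, and no hypothesis test, stopping rule or efficacy result depends on it. That bears on how much the point matters, not on whether the estimate is biased.

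**Conclusion.** The point holds in a limited form. The one-arm testing is explicit in two places in the protocol, the arms are compared, and no passage excludes or flags the affected terms. For any of them that meets the SAP's cut, the any-grade risk difference includes a detection component p0(1 - s), which overstates excess toxicity. Thyroid events are the most plausible case; lipase, amylase or glucose terms follow only if they are recorded despite the grade rule in 12.1.

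The illustrated 1.25 to 15 points rest on assumed incidence and recognition rates, and on complete detection in the experimental arm. The upper end needs a background incidence of 20%, which the documents do not suggest; with a real drug effect and 5% background, the excess is at most 3.75 points over the assumed range of s. It would be tempting to conclude that misleading thyroid and lipase contrasts will be reported. The documents show only that the plan permits them. The primary PFS analysis is not affected.

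**What to change.** In SAP 4.7, for adverse-event terms found by tests scheduled in one arm only (thyroid, amylase, lipase, glucose, calcium, LDH):

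- replace the any-grade risk difference with one limited to grade 3 or higher or serious events, an option that the section already half-states;
- present any-grade incidence descriptively;
- mark these rows in the by-arm tables as not comparable because scheduled testing was unequal.

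Keep the mark on the grade 3 or higher contrast for amylase and lipase, because protocol 10.7.1 itself envisages grade 3 values without symptoms.

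Two alternatives do not serve. A contrast of symptomatic or treated cases keeps the bias, because treatment can follow from the scheduled test. Adding blood tests to the observation arm is no longer practical: accrual closed on 30 April 2019 and the SAP is dated May 2020.

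The cost is a few lines of SAP text and a table footnote. The downside is that a few laboratory-detected events have no any-grade contrast.
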